1.2.3. Rationale for Dose Selection

Results from single ascending dose and multiple ascending dose studies in Phase 1 were utilized to select appropriate doses for Phase 2 studies. The Phase 2 study of ozanimod in UC was conducted comparing 0.92 mg and 0.46 mg of ozanimod with placebo. Safety was comparable across both ozanimod arms, and the 0.92 mg/day dose arm demonstrated better efficacy as compared to the 0.46 mg/day dose arm across various clinical and endoscopic endpoints (Sandborn, 2016). Results suggested a dose dependent efficacy response, making 0.92 mg more favorable for future investigation.

The favorable clinical results and the available safety data from the Phase 2 and Phase 3 UC studies, as described above, as well as supportive clinical and safety data from the completed Relapsing Multiple Sclerosis (RMS) program, provide additional data to support use of the 0.92 mg dose of ozanimod. Data from 52 weeks of treatment (RPC01-2201) in subjects with active CD treated with ozanimod 0.92 mg suggest clinical benefit based on clinical, endoscopic, histologic [REDACTED] responses, with a comparable safety profile to subjects previously evaluated with ozanimod. The overall data supported evaluating the 0.92 mg dose in the ozanimod CD program.

A dose escalation regimen over the first 7 days is being utilized [REDACTED]

[REDACTED] A dose escalation starting with 0.23 mg of Ozanimod for the first 4 days of dosing followed by 0.46 mg on Days 5 through 7 before progressing to the 0.92 mg/day dose will be used.

Please refer to the Investigator's Brochure for detailed information concerning the available pharmacology, toxicology, drug metabolism, clinical studies, and AE profile of the IP.

1.2.4. Benefit Risk Assessment

Despite recent progress in CD treatment, there remains an unmet need for oral agents that are safe and convenient and that can provide effective induction and long term maintenance of clinical remission. The benefit risk profile for ozanimod has been evaluated for the indication of Crohn's disease. Results from subjects with moderate to severe disease who previously failed prior therapy and were treated with ozanimod 0.92 mg daily for at least 12 weeks suggested clinical and endoscopic benefit. In addition, the safety results suggest that ozanimod is generally well tolerated in patients with Crohn's disease and is consistent with that observed in other patient populations (UC and RMS). The overall data to date suggest that this ozanimod Induction Study (RPC01-3202) has a potential favorable benefit risk profile for patients with moderate to

severe Crohn's disease who have inadequate response or intolerance to corticosteroids, immunomodulators, or biologic therapy.

The severe acute respiratory syndrome coronavirus 2 (SARS-CoV-2) global health pandemic has been identified as a potential risk to clinical trial subjects in general and may particularly affect patients with underlying chronic disease. It is not known if taking ozanimod increases the risk of SARS-CoV-2 infection, or the duration or severity of coronavirus disease 2019 (COVID-19). The individual benefit risk considerations remain the responsibility of the Investigator. Investigators should apply clinical judgment and these risks should be considered when enrolling a subject.

The exclusion criteria (Section 4.3) have been designed to exclude people with current and recent infections. Testing to exclude asymptomatic SARS-CoV-2 prior to enrollment should follow local practice.

The study has been designed with study visits that allow for close monitoring of subjects' safety throughout the clinical trial (Table 1), and subjects are encouraged to contact the investigator if an intercurrent illness develops between study visits. Testing for COVID-19 to inform decisions about clinical care during the study should follow local standard practice.

Evaluation and management of SARS-CoV-2 infections arising during the course of the trial are left to the discretion and expertise of the Investigator. For subjects who are exhibiting symptoms consistent with SARS-CoV-2, the Sponsor advises the Investigator to consider holding dosing of investigational product and to consult the Medical Monitor.

Non-live COVID-19 vaccination is considered a simple concomitant medication within the study. However, the efficacy and safety of non-live vaccines (including non-live COVID-19 vaccines) in subjects receiving Ozanimod is unknown. The individual benefit risk assessment of a vaccine remains with the Investigator. If the assessment of the Investigator suggests the vaccine to be beneficial, it must be a non-live, replication incompetent vaccine, and be approved or authorized (ie, Emergency Use Authorization [FDA] or equivalent) by national health authorities.

1.3. Study Rationale

Given the mechanism of action of ozanimod, data from the preclinical animal model, the positive results from the Phase 2 (RPC01-202) and Phase 3 (RPC01-3101) UC studies, and preliminary results from the Induction Period of the Phase 2 study in CD (RPC01-2201), a Phase 3 program with ozanimod in CD is being initiated.

The current study is designed as a double-blind, placebo-controlled study to assess the efficacy and safety of ozanimod in inducing clinical remission and response in subjects with moderately to severely active CD.

Primary efficacy assessment of ozanimod 0.92 mg per day will be assessed at Week 12 based on the efficacy results seen in the RPC01-2201 study after 12 weeks of treatment with ozanimod 0.92 mg daily.

2. STUDY OBJECTIVES AND ENDPOINTS

2.1. Study Objectives

2.1.1. Primary Objective:

- Demonstrate the efficacy of ozanimod compared to placebo on the induction of clinical remission

2.1.2. Secondary Objectives:

- Demonstrate the efficacy of ozanimod compared to placebo on induction of clinical response, endoscopic response, endoscopic remission, and histologic improvement
- Evaluate the efficacy of ozanimod compared to placebo, in subjects who had previously received biologic therapy (eg, anti-IL-12, anti-IL-23, anti-TNF, or anti-integrin therapy)
- Characterize the population pharmacokinetics (PK) and PK/pharmacodynamics (PD) relationship of ozanimod
- Demonstrate the safety and tolerability of ozanimod as induction therapy

2.2. Study Endpoints

Note: All endpoints will evaluate subjects at Week 12 unless otherwise specified.

2.2.1. Primary Endpoint:

- Proportion of subjects with a CDAI score < 150 at Week 12

[figure not shown]
2.2.2. Key Secondary Endpoints:

- Proportion of subjects with average daily abdominal pain score ≤ 1 point, and average daily stool frequency score ≤ 3 points with abdominal pain and stool frequency no worse than baseline at Week 12
- Proportion of subjects with a Simple Endoscopic Score for Crohn's Disease (SES-CD) score decrease from baseline of $\geq 50\%$ at Week 12
- Proportion of subjects with CDAI reduction from baseline of ≥ 100 points or CDAI score < 150 at Week 12
- Proportion of subjects with CDAI reduction from baseline of ≥ 100 points or CDAI score < 150 and SES-CD decrease from baseline of $\geq 50\%$ at Week 12

2.2.3. Other Secondary Endpoints:

- Proportion of subjects with CDAI score < 150 at Week 12 and SES-CD decrease from baseline of $\geq 50\%$ at Week 12
- Proportion of subjects with an average daily abdominal pain score ≤ 1 point, and average daily stool frequency score ≤ 3 points with abdominal pain and stool

- frequency no worse than baseline and an SES-CD ≤ 4 points and decrease ≥ 2 points at Week 12
- Proportion of subjects with an average daily abdominal pain score ≤ 1 point, and average daily stool frequency score ≤ 3 points with abdominal pain and stool frequency score no worse than baseline and an SES-CD decrease from baseline of $\geq 50\%$ at Week 12
 - Histologic Improvement based on differences between ozanimod and placebo in histologic disease activity scores (ie, Global Histologic Activity Score (GHAS) changes) ([Geboes, 2000](#)) at Week 12
 - Proportion of subjects with CDAI reduction from baseline of ≥ 70 points at Week 12
 - Proportion of subjects with absence of ulcers ≥ 0.5 cm with no segment with any ulcerated surface $\geq 10\%$ at Week 12
 - Proportion of subjects with a Crohn's Disease Endoscopic Index of Severity (CDEIS) decrease from baseline of $\geq 50\%$ at Week 12

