4.2. Inclusion Criteria

Subjects must satisfy the following criteria to be enrolled in the study:

1. Male or female subjects aged 18 to 75 years (at Screening)
2. Subject should not have any constraints under local regulations, must provide written informed consent prior to any study-related procedures, and must have the ability to comply with the Table of Events.
3. Subject has signs and symptoms consistent with a diagnosis of CD for at least 3 months (prior to first IP administration). The diagnosis should be confirmed by clinical and endoscopic evidence and corroborated by a histology report. (Note: endoscopy and local histopathology confirmation may be obtained during Screening if no prior report is readily available).
4. Subject has met each of the following 2 criteria:
 - a CDAI score ≥ 220 and ≤ 450
 - an average daily stool frequency ≥ 4 points and/or an abdominal pain of ≥ 2 points
5. Subject has a SES-CD score of ≥ 6 (or SES-CD ≥ 4 in subjects with isolated ileal disease).
6. Subject has an inadequate response or loss of response to or is intolerant of at least 1 of the following systemic CD treatments (see [Appendix B](#) for additional details):
 - corticosteroids
 - immunomodulators
 - biologic therapies (eg, ustekinumab, TNF α antagonists, or vedolizumab)
7. If the subject is taking the following background therapies for CD, a stable dose must be maintained throughout the study beginning from the screening period as indicated below:
 - oral aminosalicylates (eg, mesalamine, sulfasalazine, olsalazine, balsalazide) with a stable dose for at least [REDACTED] prior to Screening endoscopy
 - prednisone (doses [REDACTED]) or equivalent with a stable dose for at least [REDACTED] prior to Screening endoscopy
 - budesonide therapy (doses [REDACTED]) or beclomethasone (doses [REDACTED]) at a stable dose for at least [REDACTED] prior to the Screening endoscopy
8. Subject at high risk (ie, family history, CD duration) for colonic malignancy has documented evidence of having had a surveillance colonoscopy within the last 2 years or according to local and national medical guidelines to evaluate for polyps, dysplasia, or

malignancy. If there is no recent history of surveillance colonoscopy, this can be done as part of the colonoscopy performed during Screening. Any visualized adenomatous polyps must be removed and any suspicious lesion confirmed free of cancer and/or dysplasia prior to randomization.

9. Female subjects of childbearing potential (FCBP):

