6.3.2.2. Simple Endoscopic Score for Crohn's Disease

The SES-CD assesses the degree of inflammation. The SES-CD assesses the following four components: size of ulcers, ulcerated surface, affected surface, and presence of narrowing. Each of these components are scored on a scale of 0 to 3 as outlined in [Table 5](#).

In the SES-CD, each of these 4 components are assessed in the 5 segments of the ileum and colon: ileum, right, transverse, left (descending and sigmoid), and rectum. The SES-CD is the sum of the individual scores of each of the components across the 5 segments.

Endoscopic response has not yet been validated and may be defined as a 25% to 50% or greater decrease in SES-CD from baseline. [REDACTED]

[REDACTED], the same endoscopist and the same diameter colonoscope as used in screening should be used throughout the study wherever possible.

[REDACTED] Details regarding the biopsies are provided in the biopsy manual and Histology Image Charter. Colonoscopies will be read at a centralized reading facility in a process outlined in the Endoscopy Image Charter. Centralized reading will be the primary assessment for endoscopy; local endoscopy scores will also be collected.

Local colonoscopy may be used for baseline assessments in the Induction Study if within 35 days of baseline, consent was obtained from the subject for use in a clinical study, and video quality and format is considered adequate for evaluation by centralized reading facility.

Table 5: Definitions of Simple Endoscopic Score for Crohn's Disease (SES-CD)

Variable	SES-CD Values			
	0	1	2	3
Size of ulcers	None	Aphthous ulcers (0.1 to 0.5 cm)	Large ulcers (0.5 to 2 cm)	Very large ulcers (>2 cm)
Ulcerated surface	None	< 10%	10%-30%	>30%
Affected surface	Unaffected segment	< 50%	50%-75%	>75%
Presence of narrowings	None	Single, can be passed	Multiple, can be passed	Cannot be passed

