9.2. Study Population Definitions

The following analysis populations will be used in the statistical analysis:

- **Intent-to-Treat (ITT):** The ITT analysis population will consist of all randomized subjects from the Screened analysis population receiving at least 1 dose of IP. Subjects in the ITT analysis population will be analyzed according to the randomized treatment, regardless of the treatment actually given. The primary analysis population for all efficacy endpoints will be the ITT analysis population.
- **Safety:** The safety analysis population is defined as all subjects who are randomized and receive at least one dose of study treatment, analyzed by actual treatment received.
- **Per-protocol (PP):** The PP population will consist of all subjects in the ITT population who do not have protocol deviations that may substantially affect the primary efficacy assessment. This population will be used in a sensitivity analysis of the primary endpoint.

Additional analysis populations are defined and their use described in the SAP.

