9.6. Efficacy Analysis

Because all primary and secondary endpoints for this study are either remission or responder endpoints (ie, proportions of subjects meeting the criteria to be classified as remitters or responders for the 2 treatment groups), the analysis of endpoints using a continuous measure will not be described here, but rather discussed in the SAP. For the primary analysis of remission or responder endpoints, the ITT analysis population will be used. Furthermore, for the primary analysis of remission or responder endpoints and for a given timepoint or study visit, ITT subjects who have insufficient data for remission or response determination will be considered non-remitters/non-responders for that timepoint or study visit. Sensitivity analyses, missing data imputation and continuous endpoint efficacy analyses are discussed in the SAP.

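### The Week 12 ulcer-absence endpoint has no baseline term and entry admits subjects who already meet it, so its single ITT rate mixes clearing ulcers with staying free of them

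*Combined protocol and SAP*

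**What the plan says.** The protocol summary and Section 2.2.3 give the endpoint as "Proportion of subjects with absence of ulcers ≥ 0.5 cm with no segment with any ulcerated surface" ≥ 10% at Week 12. Neither place refers to baseline.

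Endoscopic entry (Section 4.2, criterion 5) is by total score only: "Subject has a SES-CD score of ≥ 6 (or SES-CD ≥ 4 in subjects with isolated ileal disease"). Section 6.3.2.2 forms that total by summing four components, each scored 0 to 3, over five segments. In Table 5, score 1 for ulcer size is "Aphthous ulcers (0.1 to 0.5 cm"), score 2 starts at 0.5 cm, and an ulcerated surface below 10% scores 1. Affected surface scores up to 3 whether or not ulcers are present.

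The other visible endoscopic endpoints carry a baseline term. The SES-CD and CDEIS response endpoints need a decrease of at least 50%, and the low-score endpoint ends "frequency no worse than baseline and an SES-CD ≤ 4 points and decrease ≥ 2 points at Week 12".

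On analysis, Section 9.2 states "The primary analysis population for all efficacy endpoints will be the ITT analysis population", and Section 9.6 adds that "ITT subjects who have insufficient data for remission or response determination will be considered non-remitters/non-responders for that timepoint or study visit". The treatment failure rules (Section 9.8) also apply. Section 9.6.2 names the CMH method for primary and key secondary endpoints only. Section 9.6.3 tests all other endpoints at a nominal 0.05. For endoscopy, "Centralized reading will be the primary assessment for endoscopy; local endoscopy scores will also be collected".

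**The concern.** If some subjects enter already free of such ulcers, they succeed by keeping a status, while the rest succeed only by clearing ulcers. One pooled proportion does not show which. A reader who takes it as an ulcer-clearance rate will overstate clearance in both arms whenever staying free is likelier than clearing.

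The effect on the treatment difference depends on rates the documents do not give. If already-free subjects mostly stay free in both arms, they dilute the difference. If the drug also preserves the status, they may not. In either case a strongly prognostic baseline variable is left out of the visible analysis, which costs precision.

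**Working it through.** **Is there a figure to reproduce?** Not for this endpoint. The stated 600 (2:1, 5% type I error, at least 90% power) is for CDAI remission, and its assumed rates are redacted. Back-solving with a pooled-variance chi-square, the literature placebo rate of 18% (Table 9) against 30.0% on ozanimod needs 200 placebo and 400 ozanimod subjects for 90% power. The 600 is thus plausible but cannot be verified. I use 400/200 below.

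**Can a subject enter already meeting the endpoint?** Table 5 component sums (ulcer size + ulcerated surface + affected surface, no narrowing):
- Two segments with aphthous ulcers, < 10% ulcerated and < 50% affected: 2 × (1+1+1) = 6, eligible.
- Isolated ileal disease with 50-75% affected: 1+1+2 = 4, eligible.
- Two ulcer-free segments with > 75% affected: 3+3 = 6, eligible. This case does not depend on how an ulcer of exactly 0.5 cm is scored.
- Largest such total without narrowing: 5 × (1+1+3) = 25.

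By contrast, CDAI < 150 also lacks a baseline term, but entry at CDAI ≥ 220 rules out overlap.

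**What the pooled rate contains.** Let f be the share already free, q the stay-free rate and c the clearance rate. Then rate = f·q + (1−f)·c. With f = 0.20, q = 0.75 and c = 0.10 on placebo: 0.15 + 0.08 = 23%, against a clearance rate of 10%.

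Share of placebo successes already free = f·q / (f·q + (1−f)·c). With c = 0.10 and q from 0.70 to 0.80:

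| f | 1% | 2% | 5% | 10% | 20% | 30% |
|---|---|---|---|---|---|---|
| Share | 7-8% | 12-14% | 27-30% | 44-47% | 64-67% | 75-77% |

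**Power, unstratified → stratified by baseline ulcer status.** Simulated trials, 400/200, binomial baseline counts, Mantel-Haenszel chi-square without continuity correction, two-sided 0.05, other strata ignored. Rates are ozanimod/placebo and all are assumptions.

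| Clear | Stay free | f = 10% | f = 20% | f = 30% |
|---|---|---|---|---|
| 20/10 | 80/80 | 70.8 → 81.5 | 53.2 → 70.3 | 39.1 → 56.9 |
| 20/10 | 85/75 | 80.0 → 89.3 | 72.5 → 88.4 | 67.6 → 87.9 |
| 20/10 | 90/70 | 87.2 → 94.3 | 87.1 → 96.9 | 88.6 → 98.4 |
| 20/10 | 60/60 | 74.1 → 79.2 | 57.2 → 65.1 | 42.0 → 50.3 |
| 20/10 | 50/50 | 75.6 → 78.7 | 59.8 → 64.6 | 45.0 → 49.9 |
| 30/20 | 60/60 | 62.8 → 65.3 | 50.0 → 53.6 | 39.3 → 42.4 |
| 30/20 | 50/50 | 63.9 → 65.1 | 51.9 → 53.7 | 39.8 → 41.7 |

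In the first three rows the gain is 7 to 11 points at f = 10% and 10 to 20 at f = 20-30%. In the last four it is about 1 to 5 and 2 to 8. At f = 1-2% it runs from under 1 to about 2 points. With no effect in either group (10% clearing, 75% staying free in both arms), the stratified test rejected in 4.9-5.1% of trials.

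**Precision of a clearance estimate.** Half-width of the 95% CI = 1.96 × √[0.16/(400(1−f)) + 0.09/(200(1−f))]. This is 5.7 points at f = 0, 6.0 at f = 10%, 6.4 at f = 20% and 6.8 at f = 30%.

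**The case against.** A Week 12 status is a legitimate estimand. The protocol lists endoscopic remission among its objectives, never labels this endpoint clearance, and covers change from baseline with the SES-CD and CDEIS endpoints. That stands: the definition is not wrong, and the point concerns how its result can be read.

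The power argument rests on unknown rates. Missing data and treatment failures count as non-success, so stay-free rates of 50-60% are plausible, and the gain is then small even at f = 20-30%. This also stands and limits the claimed size; the argument about interpretation does not need a power gain.

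Much is unseen. The SAP text is not in the public file, and Section 9.2 says "Additional analysis populations are defined and their use described in the SAP". Exclusion criteria 22-35, Sections 2.2.4-2.2.6 and the stratification factors are not visible, and no test is named for this endpoint. The recommendation is therefore conditional.

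A reader might infer that already-free subjects are automatic successes or that the comparison is biased. The documents do not support either. Such subjects must still be free at Week 12, have sufficient data and meet no treatment failure rule. Randomisation balances baseline status in expectation, so the unstratified test remains valid.

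**Conclusion.** The point holds as a modest matter of interpretation and precision. On the visible text the endpoint has no baseline term, entry does not keep out subjects who already meet it, and the pooled ITT rate cannot be read as ulcer clearance. Stratifying raised power in every scenario tested with type I error at about 5%, but the size is unknown because f and all rates are assumptions. The gain is substantial only when f is not small and staying free is much likelier than clearing (for example 70-90% against 10-20%); it is small when the rates are closer (for example 50-60% against 20-30%).

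It would go too far to infer that the endpoint is certainly underpowered, that the sponsor's analysis omits this, or that the trial's main conclusions are at risk. The endpoint is tested at nominal alpha outside the hierarchy, and the SAP may already deal with it.

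**What to change.** Before unblinding, and unless the SAP already does this:

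1. Keep the all-ITT analysis of the endpoint.
2. Add baseline ulcer status (any ulcer ≥ 0.5 cm, or any segment with ulcerated surface ≥ 10%, yes/no) as a stratification factor in whatever test is used for this endpoint.
3. Prespecify reporting by that status. The result in subjects who had such ulcers at baseline, with non-responder imputation, is the clearance estimate.
4. Define status from the centrally read baseline component scores by the same rule as at Week 12. State which score holds an ulcer of exactly 0.5 cm, since Table 5 lists that size under both score 1 and score 2.
5. State how a missing central baseline score is handled. Local scores are collected and could serve, but that would mix readers when central reading is primary.

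If the SAP already covers these steps, align the protocol wording.

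The cost is low: a wording change using scores already read at screening. The downsides are one more stratum on top of the redacted factors, sparse if f is small, and a smaller denominator for the clearance estimate (half-width about 6.0 instead of 5.7 points at f = 10%).

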2.2.7. Overview of Key Safety Assessments

The incidence, severity, relationship, and type of treatment-emergent adverse events (TEAEs), serious adverse events (SAEs), AEs leading to discontinuation of IP (see Section 14), and AESIs will be summarized, as well as clinically meaningful changes from baseline [REDACTED], [REDACTED], clinical laboratory measures, vital signs, and electrocardiograms.

